12.1.5 Handling of Dropouts or Missing Data (including outside the limits of quantification)

For laboratory parameters:

Values below the lower limit of quantification (LLOQ) will be imputed using LLOQ/2. For values above the upper limit of quantification (ULOQ), the ULOQ will be imputed.

The number of values below LLOQ or above ULOQ will be presented in each summary table. If 50% or more data are below LLOQ or above ULOQ, only the number (%) of value below LLOQ or above ULOQ will be reported in the summaries, together with minimum and maximum of the observed values.

Missing data at Baseline will not be imputed.

For BoExp:

- A last observation carried forward (LOCF) approach will be implemented to replace all missing data with the last available data for each parameter being assessed.
- For parameters assessed at several timepoints during a visit, the last available data at the timepoint being assessed collected at previous study visit will be used in the analyses. For example, if on Day 5, the evening assessment (20:00-23:00) is missing for COHb, the evening assessment from Day 4 will be used for analysis regardless whether other COHb assessments are available at Day 5.

For daily product use data in safety summaries:

- Product use categories will be defined based on percentage of THS 2.2 Menthol use calculated by averaging non missing consumption data over the entire ambulatory time interval.

For daily product use data in non-safety analyses and summaries:

- If at least 75% of the daily product use assessments over a period are available, with no more than 7-days of consecutive missing data:
 - Product use categories will be defined based on percentage of THS 2.2 use calculated by averaging non missing consumption data over the analysis interval.
 - Compliance to randomized product will be defined based on the available product use data.
- If less than 75% of the daily product use assessments over a period are available, or product use data is missing over a period of more than 7 consecutive days:
 - Product use categories will be defined based on percentage of THS 2.2 use calculated by considering the missing product use data as the CC use reported at Baseline.
 - Compliance to randomized product will be defined by considering the missing product use data as the CC use reported at Baseline.

For MNWS, QSU-brief, and MCEQ questionnaire data:

- Total scores and domain or subscale scores will be derived by averaging the individual non-missing item scores if at least 50% are non-missing, otherwise they will be set to missing.

For missing or partial dates:

- Missing dates for Day 30, 60, and Day 90 Visits will be imputed for the calculation of product use exposure within periods by adding 30, 60, or 90 days to the randomization date. If the imputed date falls after discharge date (e.g. for early terminated subjects), then the discharge date will be used.
- Missing or Partial dates will not be imputed for Adverse Events (AEs), for medical history, and for concomitant medications, but assumptions will be made as follows to assign them to specific analysis categories:

Date information (*)	AE Category	Disease Category	Medication Category
Missing date or Partial date, (e.g., --May2012, or ----2011) if month/year is the same as, or later than the month and/or year of Screening.	Product-emergent	Concomitant disease	Concomitant medication
Partial date, (e.g., --May2012, or ----2011). If month and/or year is earlier than the month and/or year of Screening.	Not product-emergent	Medical history	Prior medication

(*) Missing or partial date refers to stop date for disease and medication categories

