8 SAMPLE SIZE JUSTIFICATION

The following discussion addresses the ability to demonstrate on Day 5 a reduction of at least 50% on four selected primary BoExps and on Day 90 on a fifth primary BoExp in smokers switching from mCC to THS 2.2 Menthol as compared to smokers continuing to smoke mCC.

Table 11 describes the expected coefficients of variation (CV) and mean ratios (MR) between THS 2.2 Menthol and the two control arms in COHb, 3-HPMA, MHBMA and S-PMA on Day 5 based on data from a controlled, randomized, open-label, 3-arm parallel single-center confinement study to investigate exposure to selected smoke constituents in smokers switching from CCs to smoking article (SMAR) cigarettes for 5 days, the YVD-CS01-EU study (ClinicalTrials.gov: ID: NCT00812279) sponsored by PMI. The mean ratios and CVs for SMAR/CC are expected to be the same as THS 2.2 Menthol/mCC.

Table 11: Coefficients of Variation (YVD-CS01-EU study)

	THS 2.2 /CC MR (CV)	THS 2.2 /SA MR (CV)
COHb	0.40 (0.32)	2.10 (0.20)
3-HPMA	0.30 (0.50)	1.70 (0.33)
MHBMA	0.15 (0.70)	1.00 (0.35)
S-PMA	0.20 (0.70)	1.15 (0.42)

Abbreviations: 3-HPMA = 3-hydroxypropylmercapturic acid; CC = conventional cigarettes; COHb = carboxyhemoglobin; CV = coefficients of variation; MHBMA = monohydroxybutenyl mercaturic acid; MR = mean ratios; S-PMA = S-phenylmercapturic acid; SA = smoking abstinence; THS 2.2 = Tobacco Heating System 2.2.

Table 12 describes the expected CV and MR between THS 2.2 Menthol and the mCC control arm in Total NNAL on Day 90 based on data from a Philip Morris USA-sponsored randomized, controlled, switching, open-label, parallel-group, single-center study in 90 male and female adult smokers evaluated six biomarkers of tobacco smoke exposure over a 12-week period (Frost-Pineda et al., 2008). The mean ratios and coefficients of variations for EHCJLI /CC are expected to be the same as THS 2.2 Menthol/mCC.

Table 12: Expected Mean Ratios and Coefficients of Variation for THS 2.2 Menthol/mCC

	THS 2.2 Menthol/mCC MR (CV)
Total NNAL	0.30 (0.60)

Abbreviations: Total NNAL = total 4-(methylnitrosamino)-1-(3-pyridyl)-1-butanol; MR = mean ratios; THS 2.2 = Tobacco Heating System 2.2.

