**Table 15: Expected Power (YVD-CS01-EU and ZRHX-EX-01 Studies Assumptions)**

Assumptions	Reduction					
	50%	51%	52%	53%	54%	55%
YVD-CS01-EU	94%	88%	81%	70%	56%	38%
ZRHX-EX-01	98%	97%	92%	76%	41%	6%

A total of 160 smokers (80 in THS 2.2 Menthol, 40 in mCC, and 40 in the SA arms) were to be randomized over both sites. However due to the site that terminated due to ICH/GCP non-compliance 219 smokers were randomized, so that the 160 smokers would be recruited at the Tokyo Heart Center, to demonstrate a reduction of at least 50% on all 5 primary BoExp in smokers switching from mCC to THS 2.2 Menthol as compared to those continuing to smoke mCC, using one-sided test with 2.5% type I error probability. The calculation of the sample size was based on the assumption that 50% of the subjects in the THS 2.2 Menthol arm would be using THS 2.2 Menthol exclusively at Day 90.

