10.1 Full Analysis Set

The FAS consists of all the randomized subjects who had at least one post-randomization product use experience, if randomized to THS 2.2 Menthol or mCC, and have at least one valid non-safety assessment (THS 2.2 Menthol, mCC, and SA arms). Subjects that were enrolled at the site that terminated due to ICH/GCP non-compliance will be excluded from the FAS.

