12.6.1.3 Sensitivity Analysis

As a sensitivity analysis, the ANCOVA model described in Section 12.6.1.1 "Analysis of Biomarkers of Exposure for Primary Objectives" will be repeated for the PP Set at Day 5 and Day 90 data by means of a mixed model approach, without the LOCF data imputation described in Section 12.1.5 "Handling of Dropouts or Missing Data (including outside the limits of quantification)". Any data outside of the allowed time window (see Table 18: Assessment Windows) on Days 5 and 90 will be excluded from the analysis.

The SAS code to be used for the THS 2.2 Menthol and mCC data is shown below:

```
Proc mixed data=_data_;
  Class randomization_arm sex cigarette_cons;
  Model log_biomarker = log_baseline sex cigarette_cons
    randomization_arm;
  Lsmean randomization_arm / pdiff =control('mCC') alpha=0.05 cl;
  Run;
```

An additional sensitivity analysis will be produced for the primary analysis, summaries and graphs of the COHb, MHBMA, 3-HPMA, S-PMA and Total NNAL will be repeated for the compliant population for THS 2.2 Menthol vs mCC. The analysis will use the same model as described in Section 12.6.1.1 "Analysis of Biomarkers of Exposure for Primary Objectives"

The data will be presented in the below outputs:

TFL number	Title
FIGURES	
15.1.1.3	Biomarker of Exposure Arithmetic Mean and 95% CI for Percent Change from Baseline – Compliant Population
TABLES	
15.2.3.1.2	Sensitivity Analysis of COHb, MHBMA, 3-HPMA, S-PMA and Total NNAL on Day 5/90 Visit for THS 2.2 Menthol versus mCC for the Primary Objective using Mixed Model – PP Set
15.2.3.1.3	Sensitivity Analysis of COHb, MHBMA, 3-HPMA, S-PMA and Total NNAL on Day 5/90 Visit for THS 2.2 Menthol versus mCC for the Primary Objective – Compliant Population
15.2.4.1.3	Descriptive Statistics of Blood COHb (%) – Compliant Population
15.2.4.2.3	Descriptive Statistics of MHBMA in 24-hour Urine Collection – Compliant Population
15.2.4.3.3	Descriptive Statistics of 3-HPMA in 24-hour Urine Collection – Compliant Population
15.2.4.4.3	Descriptive Statistics of S-PMA in 24-hour Urine Collection – Compliant Population
15.2.4.5.3	Descriptive Statistics of Total NNAL in 24-hour Urine Collection – Compliant Population

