12.6.2 Secondary Analyses

The analysis of COHb, MHBMA, 3-HPMA, and S-PMA at Day 90 and Total NNAL at Day 5 will be repeated for the PP Set.

The analysis of the COHb, MHBMA, 3-HPMA, S-PMA at Day 5/ Day 90 and Total NNAL at Day 90 will be repeated for the FAS as described in Section 12.6.1.1 "Analysis of Biomarkers of Exposure for Primary Objectives". These endpoints will also be

examined to compare the reductions in THS 2.2 Menthol vs. SA using the same methodology as for the primary analysis for the PP Set.

The baseline is for the biomarkers measured in urine is as defined in Section 12.1.4 "Definitions for Statistical Data Analysis".

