15.2.3.6	Analysis of Additional Biomarkers of Exposure versus mCC and SA using Mixed Model on Day 5/90 Visit – PP Set
15.2.3.7	Analysis of Additional Biomarkers of Exposure versus mCC and SA on Day 5/90 Visit– Compliant Population
15.2.4.1.2	Descriptive Statistics of Blood COHb (%) – FAS
15.2.4.1.3	Descriptive Statistics of Blood COHb (%) – Compliant Population
15.2.4.2.2	Descriptive Statistics of MHBMA in 24-hour Urine Collection – FAS
15.2.4.2.3	Descriptive Statistics of MHBMA in 24-hour Urine Collection – Compliant Population
15.2.4.3.2	Descriptive Statistics of 3-HPMA in 24-hour Urine Collection – FAS
15.2.4.3.3	Descriptive Statistics of 3-HPMA in 24-hour Urine Collection – Compliant Population
15.2.4.4.2	Descriptive Statistics of S-PMA in 24-hour Urine Collection – FAS
15.2.4.4.3	Descriptive Statistics of S-PMA in 24-hour Urine Collection – Compliant Population
15.2.4.5.2	Descriptive Statistics of Total NNAL in 24-hour Urine Collection – FAS
15.2.4.5.3	Descriptive Statistics of Total NNAL in 24-hour Urine Collection – Compliant Population
15.2.4.6.1	Descriptive Statistics of Exhaled CO (ppm) – PP Set
15.2.4.6.2	Descriptive Statistics of Exhaled CO (ppm) – FAS
15.2.4.7.1	Descriptive Statistics of 1-OHP in 24-hour Urine Collection – PP Set
15.2.4.7.2	Descriptive Statistics of 1-OHP in 24-hour Urine Collection – FAS
15.2.4.8.1	Descriptive Statistics of Total NNN in 24-hour Urine Collection – PP Set
15.2.4.8.2	Descriptive Statistics of Total NNN in 24-hour Urine Collection – FAS
15.2.4.9.1	Descriptive Statistics of 4-ABP in 24-hour Urine Collection – PP Set
15.2.4.9.2	Descriptive Statistics of 4-ABP in 24-hour Urine Collection – FAS
15.2.4.10.1	Descriptive Statistics of 1-NA in 24-hour Urine Collection – PP Set
15.2.4.10.2	Descriptive Statistics of 1-NA in 24-hour Urine Collection – FAS
15.2.4.11.1	Descriptive Statistics of 2-NA in 24-hour Urine Collection – PP Set
15.2.4.11.2	Descriptive Statistics of 2-NA in 24-hour Urine Collection – FAS
15.2.4.12.1	Descriptive Statistics of o-tol in 24-hour Urine Collection – PP Set
15.2.4.12.2	Descriptive Statistics of o-tol in 24-hour Urine Collection – FAS
15.2.4.13.1	Descriptive Statistics of CEMA in 24-hour Urine Collection – PP Set
15.2.4.13.2	Descriptive Statistics of CEMA in 24-hour Urine Collection – FAS
15.2.4.14.1	Descriptive Statistics of HEMA in 24-hour Urine Collection – PP Set
15.2.4.14.2	Descriptive Statistics of HEMA in 24-hour Urine Collection – FAS

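### The secondary FAS Day 90 biomarker analyses can carry supervised Day 5 values forward, and no planned FAS analysis shows the result without them

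*SAP*

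**What the plan says.** **The rule.** For BoExp, SAP 12.1.5 states that "A last observation carried forward (LOCF) approach will be implemented to replace all missing data with the last available data". Missing Baseline values are not imputed. No limit is set on the gap, and crossing from confinement to the ambulatory period is not barred. Protocol 12.1.4 is equally open.

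**Who can be carried.** SAP 10.1 admits a randomized subject to the FAS with one post-randomization product use (THS and mCC arms) and one valid non-safety assessment; no ambulatory sample is needed. Under Protocol 9.5, early termination repeats the Day 6 safety assessments. The urine bottle closed on Day 6 is the Day 5 collection (Protocol Table 16), so no later urinary value is specified for someone who leaves before the Day 30 Visit.

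**Where the carried value is used.** SAP 12.6.2 says that the analysis of COHb, MHBMA, 3-HPMA and S-PMA "at Day 5/ Day 90 and Total NNAL at Day 90 will be repeated for the FAS", by the method of 12.6.1.1. Table 15.2.3.3 reports this, and Table 15.2.3.5 does the same for the other BoExp.

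**Where LOCF is switched off.** In SAP 12.6.1.3 the ANCOVA "will be repeated for the PP Set at Day 5 and Day 90 data by means of a mixed model approach", without LOCF. For the other markers, Table 15.2.3.6 is titled "Analysis of Additional Biomarkers of Exposure versus mCC and SA using Mixed Model on Day 5/90 Visit", again for the PP Set. The compliant-population repeat is a subset of the PP Set and keeps the 12.6.1.1 model.

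**Expected use.** SAP 8 bases the sample size on the assumption that "50% of the subjects in the THS 2.2 Menthol arm would be using THS 2.2 Menthol exclusively at Day 90".

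**The concern.** A Day 5 value comes from a subject whose product was handed out one item at a time (Protocol 6.5.4). By Day 90 the sponsor expects only half of the THS arm to be exclusive users, so a Day 5 value need not be typical of the FAS at that time. For markers that clear within a day, carrying it forward answers one question only: what exposure would be if every leaver had stayed an exclusive THS user.

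Section 12.1.5 treats the same kind of subject quite differently in the diary. Where too much product-use data are missing, "Compliance to randomized product will be defined by considering the missing product use data as the CC use reported at Baseline". One subject can thus be taken as smoking at baseline level for compliance and as a supervised THS user for biomarkers.

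The FAS repeat is the planned Day 90 BoExp analysis that does not select on compliance, so a reader will look there for the less idealised ratio. Nothing planned shows how far that ratio depends on carried values.

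**Working it through.** **1. Inputs.** SAP Table 11 gives THS/mCC ratios r (CV) of COHb 0.40 (0.32), 3-HPMA 0.30 (0.50), S-PMA 0.20 (0.70) and MHBMA 0.15 (0.70), and THS/SA ratios of 2.10, 1.70, 1.15 and 1.00 in the same order. SAP 8 justifies their use: "The mean ratios and CVs for SMAR/CC are expected to be the same as THS 2.2 Menthol/mCC". Table 12 gives Total NNAL 0.30 (0.60) at Day 90, and Protocol 4.2 gives its half-life as 10 to 15 days. Table 14 gives 80:40 subjects (40:40 for NNAL).

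**2. The plan's own figure.** Take SD = √ln(1+CV²), SE = SD·√(1/n₁+1/n₂) and power = Φ(ln(0.5/r)/SE − 1.96). This gives COHb 95.8%, 3-HPMA 99.99%, S-PMA and MHBMA about 100%, and NNAL 98.5%. The product is 94.3%, against 94% in Table 15. With the Table 13 inputs it is 98.2%, against 98%. Some columns for larger reductions do not reproduce closely with this approximation, but nothing below uses them.

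**3. Short half-life markers.** Let q be the share of THS FAS subjects whose Day 90 value is carried from Day 5. On the log scale,

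LOCF mean / true mean = (carried level / leavers' true Day 90 level)^q.

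The carried level is r, with mCC = 1. The true level is 1 if leavers resumed mCC, r if they stayed on THS, and r/(THS/SA) if they abstained. With q = 0.10 (8 of 80, assumed):

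| Marker | Resumed mCC: r^0.10 | Stayed on THS | Abstained: (THS/SA)^0.10 |
|---|---|---|---|
| COHb | 0.912 | 1 | 1.077 |
| 3-HPMA | 0.887 | 1 | 1.054 |
| S-PMA | 0.851 | 1 | 1.014 |
| MHBMA | 0.827 | 1 | 1.000 |

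If leavers resumed mCC, the range across markers is 0.955 to 0.910 at q = 0.05 and 0.833 to 0.684 at q = 0.20. If leavers behaved like the remaining THS subjects, the error lies between the first two columns. Its size turns on how much the non-exclusive half smoke, which the documents do not state.

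**4. Total NNAL.** It has barely fallen by Day 5: 0.3 + 0.7·0.5^(5/t) = 0.795 (t = 10 days) or 0.856 (t = 15 days).
- Leavers resumed mCC: 0.795^0.10 = 0.977 and 0.856^0.10 = 0.985, so 1.5-2.3% too low.
- Leavers stayed on THS: (0.795/0.30)^0.10 = 1.102 and (0.856/0.30)^0.10 = 1.110, so 10-11% too high.

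**5. Does the secondary test move?** The secondary hypothesis is only that THS is below mCC. Take a harsh case: 20% of the THS arm leave and resume mCC, and half of those who stay are also at full mCC exposure. The true THS mean log ratio is 0.8·0.5·ln r. For COHb:
- mean = 0.4·ln 0.40 = −0.367
- THS variance = 0.0975 + 0.4·0.6·(ln 0.40)² = 0.299
- SE = √(0.299/80 + 0.0975/40) = 0.0786
- z = 4.66, so power = Φ(4.66 − 1.96) = 99.7%

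The same steps give z = 4.27 for 3-HPMA and S-PMA and 4.73 for MHBMA, so power is about 99% or more without any carrying. Under LOCF the mean log ratio becomes 0.6·ln r with the same variance, so z is 1.5 times as large. The test is passed either way.

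**6. Which COHb value is carried?** For parameters with several timepoints per visit, 12.1.5 takes the same timepoint from the previous visit. Table 18 places the Day 90 COHb sample from 10:00 to 12:30. The Day 5 samples are before first product use, 12:00-13:30, 16:00-17:30 and 20:00-21:30. None matches exactly, so the rule does not say which Day 5 value stands in. Urinary markers are not affected.

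**The case against.** **No planned conclusion turns on this.** The 50% criterion applies to the five primary endpoints on the PP Set, and step 5 shows the secondary test passing in a harsh case. SAP 10 says that the aim is the optimal effect in compliant users and leaves real-world effect to other studies. This stands, and it limits the point to the size of a supportive estimate.

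**The extent of missing data will be visible.** SAP 12.1.3 reports the number and percent of subjects with missing data, and 12.2 tabulates visit completion and reasons for discontinuation. This stands too, but those tables show how many values are missing, not what carrying them does to the ratio.

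**The largest errors come from the least supported scenario.** Under Protocol 5.1.3, smoking cigarettes in the ambulatory period is not a reason for withdrawal, whereas a wish to quit requires withdrawal in the THS and mCC arms. Leavers may therefore lean towards abstinence, where LOCF works against THS. A reader might infer that LOCF here flatters THS; the documents do not support a fixed direction.

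**An observed-data model knows nothing about these subjects after Day 5.** True. It replaces one assumption with another, and its use is to show whether the ratio is sensitive to the choice.

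**Conclusion.** The gap is real and small. Carry-forward is unlimited, FAS membership does not need an ambulatory sample, and each BoExp model stated to omit LOCF is on the PP Set. The FAS Day 90 ratios therefore have no version without carried values.

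At an assumed 10% early departure from the THS arm, the geometric mean for the short half-life markers would be between about 17% too low and 8% too high, depending on what leavers did. Total NNAL would be between about 2% too low and 10-11% too high. These figures rest on the Table 11 and 12 ratios and on a dropout rate that the documents do not give. The effect is zero if nobody leaves before Day 30.

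A reader might infer that the confirmatory result is at risk. The documents do not support that. Four of the five primary endpoints are read on Day 5, and the PP Set already has a model without LOCF. A THS subject with a sparse diary is counted as smoking at baseline level, which points to exclusion from the PP Set, and a carried Day 5 NNAL value is high, so it works against showing a reduction. This is a worthwhile, low-cost addition and not a flaw in the primary analysis.

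**What to change.** Leave the primary PP ANCOVA and the planned FAS LOCF tables as they are. For the FAS at Day 90, add:

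1. **An observed-data sensitivity analysis without LOCF.** Fit a repeated-measures model to Days 30, 60 and 90 with log baseline, sex, consumption stratum, arm, visit and arm-by-visit, and an unstructured within-subject covariance. Report the Day 90 contrasts. Exhaled CO stays untransformed, as in SAP 12.6.2.1. The PROC MIXED code in 12.6.1.3 has no repeated term, so it needs a line such as `repeated visit / subject=id type=un`.
2. **A count of carried-forward Day 90 values** by arm and source visit (Day 5 or earlier, Day 30, Day 60). This alone tells the reader whether the matter is live.
3. **One sentence in 12.1.5** stating which confinement COHb value, if any, stands in for a missing Day 90 sample.

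An analysis using the subject's own baseline where no ambulatory sample exists may be added, labelled as a return-to-smoking scenario.

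The cost is SAP wording, a few lines of SAS, an observed-data companion to each of the two FAS tables, and one count table. No new data are needed, and the confirmatory model does not change. The downside is that subjects with no ambulatory sample contribute nothing to the model in item 1, which assumes that they resemble similar subjects who stayed.

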5.2 Secondary Objectives and Endpoints

1. To evaluate self-reported nicotine/tobacco product use including dual-use in an ambulatory setting in smokers switching from mCC to THS 2.2 Menthol as compared to smokers continuing to smoke mCC and to smoking abstinence (SA).

Endpoint:

- Number of mCC or Menthol Tobacco Sticks used daily as reported on the log during the confinement period and self-reported number of any nicotine/tobacco product use on a daily basis as reported on the product use electronic diary.

2. To determine the reduction of secondary BoExp in a confinement setting and in an ambulatory setting in smokers switching from mCC to THS 2.2 Menthol as compared to smokers continuing to smoke mCC.

Endpoints:

- Quantity Excreted in urine over 24 hours for MHBMA, S-PMA and 3-HPMA.
- Carbon monoxide (CO) (expressed as ppm) in exhaled breath.

- Urinary BoExp (expressed as quantity excreted and concentration adjusted for creatinine) in 24-hour urine on Day 5 and on Day 90 Visit:
 - Total 1-hydroxypyrene (1-OHP),
 - Total N-nitrosonornicotine (NNN),
 - 4-aminobiphenyl (4-ABP),
 - 1-aminonaphthalene (1-NA),
 - 2-aminonaphthalene (2-NA).
 - O-toluidine (o-tol).
 - 2-cyanoethylmercapturic acid (CEMA).
 - 2-hydroxyethyl mercapturic acid (HEMA).
 - 3-hydroxybenzo(a)pyrene (B[a]P).
 - 3-hydroxy-1-methylpropyl-mercapturic acid (HMPMA).
 - S-benzylmercapturic acid (S-BMA).

3. To describe the levels of primary and secondary BoExp over the entire exposure period (confinement and ambulatory periods) in smokers switching from mCC to THS 2.2 Menthol as compared to smokers continuing to smoke mCC and to SA.

Endpoints (on Days 1 to 5, Day 30 Visit, Day 60 Visit and Day 90 Visit):

- CO (expressed as ppm) in exhaled breath.
- COHb in blood (expressed as % saturation of Hemoglobin).
- Urinary BoExp (expressed as quantity excreted and concentration adjusted for creatinine) in 24-hour urine:
 - MHBMA.
 - 3-HPMA.
 - S-PMA.
 - Total NNAL.
 - 1-OHP.
 - Total NNN.
 - 4-ABP.
 - 1-NA.
 - 2-NA.
 - o-tol.
 - CEMA.
 - HEMA.
 - B[a]P.
 - HMPMA.
 - S-BMA.

4. To determine the levels of nicotine over the entire exposure period (confinement and ambulatory periods) in smokers switching from mCC to THS 2.2 Menthol as compared to smokers continuing to smoke mCC and to describe their levels over the entire exposure period.

Endpoints:

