12.5 Extent of Exposure (Product Consumption)

Details of the product test prior to enrollment and of product use after randomization will be listed and summarized. During the confinement period the daily usage, as recorded in the log, will be summarized by randomization arm.

The maximum and average daily usage of the assigned product and non-assigned product will be summarized over the whole ambulatory period, as recorded by the subject, and for each of the periods 2 to 4 (see section 10.2 “Per Protocol Set”).

All summaries will be produced for the Safety Population, and for the PP Set at periods 1 to 4. Summaries of data in Ambulatory will also be repeated for the FAS, if the population differs from the Safety population by more than 10%.

In addition the number and percentage of subjects falling into each product use category (see Section 6.3.3.1 “Dual-use”) during the ambulatory period will be presented.

The average product use data will also be presented by randomized product and by product use categorization (see Section 6.3.3.1 “Dual-use”).

The data will be presented in the below outputs:

TFL number	Title
TABLES	
15.2.2.1.1	Summary of Daily Product Use in Confinement Period – Safety Population
15.2.2.1.2	Summary of Daily Product Use in Confinement Period – FAS
15.2.2.1.3	Summary of Daily Product Use in Confinement Period – PP Set
15.2.2.2.1	Summary of Maximum Daily Product Use in Ambulatory Period– Safety Population
15.2.2.2.2	Summary of Maximum Daily Product Use in Ambulatory Period– FAS

TFL number	Title
15.2.2.2.3	Summary of Maximum Daily Product Use in Ambulatory Period– PP Set
15.2.2.3.1	Summary of Average Daily Product Use in Ambulatory Period– Safety Population
15.2.2.3.2	Summary of Average Daily Product Use in Ambulatory Period – FAS
15.2.2.3.3	Summary of Average Daily Product Use in Ambulatory Period – PP Set
15.2.2.4.1	Summary of Product Use by Product Use Category in Ambulatory Period – Safety Population
15.2.2.4.2	Summary of Product Use Category in Ambulatory Period – FAS
15.2.2.4.3	Summary of Product Use Category in Ambulatory Period – PP Set
15.2.2.5.1	Summary of Average Daily Product Use by Product Use Category in Ambulatory Period – Safety Population
15.2.2.5.2	Summary of Average Daily Product Use by Product Use Category in Ambulatory Period – FAS
15.2.2.5.3	Summary of Average Daily Product Use by Product Use Category in Ambulatory Period – PP Set
LISTINGS	
15.3.2.1	Listing of Product Usage

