12.6.3.9 Product preference analysis

The product preference as asked at admission will serve as a sensitivity analysis for the product exposure.

All summaries will be produced for the FAS.

These data will also be presented categorized separately by product preference and by product use categorization during periods 2-4 (see Section 6.3.3.1 “Dual-use”).

The data will be presented in the below outputs:

TFL number	Title
TABLES	
15.2.4.49	Summary of Average Daily Product Use in Ambulatory Period by Preferred Product Declared at Admission – FAS
15.2.4.50	Summary of Product Use Categories by Preferred Product Declared at Admission – FAS

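### Filling long diary gaps with baseline cigarette use can label a THS-arm subject who reported no cigarettes as Dual or CC in the descriptive product-use categories

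*SAP*

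**What the plan says.** The first secondary objective (SAP 5.2) concerns product use, including dual use. Its ambulatory endpoint is the "self-reported number of any nicotine/tobacco product use on a daily basis as reported on the product use electronic diary". SAP 6.3.3.1 turns the diary into a THS percentage (THS sticks over THS sticks plus CC, from reported consumption), and Table 20 cuts it into general categories: THS at 70% or above, Dual between 30% and 70%, CC at 30% or below. The detailed scheme reserves 'Primarily THS' for shares above 95%.

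SAP 12.1.5 has two rules for missing diary days.

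- Safety summaries: the percentage is "calculated by averaging non missing consumption data over the entire ambulatory time interval".
- All other outputs, introduced by the words "For daily product use data in non-safety analyses and summaries": small gaps are again handled from the available days. Once fewer than three quarters of a period's diary days are present, or a run longer than 7 days is absent, the percentage is instead "calculated by considering the missing product use data as the CC use reported at Baseline". The same fill applies to compliance: "Compliance to randomized product will be defined by considering the missing product use data as the CC use reported at Baseline".

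The categories appear in SAP 12.5, which plans "the number and percentage of subjects falling into each product use category" in the ambulatory period; in SAP 12.6.3.9, Table 15.2.4.50, "Summary of Product Use Categories by Preferred Product Declared at Admission – FAS"; and in SAP 12.6.3.2, where smoking-topography results on the FAS are shown by product use category.

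**The concern.** Treating missing days as full smoking is a cautious choice when the question is whether a subject may enter the PP Set. The same fill, however, also sets the descriptive category. There the question is what subjects reported using, and a filled day was not reported. No missing category and no reported-days companion table is planned for the non-safety summaries, so a reader cannot separate subjects who recorded cigarettes from subjects who stopped recording.

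This matters because Protocol 12.3 presents dual use as evidence that a regulator's draft guidance asks for. In a category table built this way, part of the Dual and CC counts may be diary non-completion.

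**Working it through.** **Inputs**

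- Trigger, fill and scope: SAP 12.1.5.
- Percentage formula: SAP 6.3.3.1. Cut-offs and periods: SAP Table 20.
- Period length L: nominally 25 days for Period 2 (Day 6 to Day 30) and 30 days for Periods 3 and 4. Visits may move by 3 days (SAP Table 18).
- Minimum baseline use: 10 mCC per day (SAP 6.2.1, inclusion criterion 5).
- Compliance limit: more than 2 CC on any one day is non-compliance (SAP Table 16).
- Assumption: r = THS sticks per reported day divided by baseline CC per day. The documents give no value, so 0.5 to 1.5 is shown.
- Reading: zero THS on filled days. The SAP states only the CC value; zero is the natural reading.

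The plan states no figure on this point to reproduce.

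**Formula.** Take a THS-arm subject with no reported CC, m missing days and baseline use c. THS total = r·c·(L−m) and CC total = c·m, so c cancels:

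%THS = 100·r·(L−m) / [r·(L−m) + m]

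The label leaves THS when r < (7/3)·m/(L−m), and becomes CC when r ≤ (3/7)·m/(L−m).

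**Where the trigger falls.** In 30 days, 7 missing leaves 23/30 = 76.7% and does not trigger; 8 missing leaves 22/30 = 73.3% and does. In 25 days, 6 missing leaves 76.0% (not triggered) and 7 leaves 72.0% (triggered).

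**Results at r = 1**, where %THS = 100·(L−m)/L:

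- 30 days: m = 8 gives 73.3% (THS); 9 gives 70.0% (THS); 10 gives 66.7% (Dual); 20 gives 33.3% (Dual); 21 gives 30.0% (CC).
- 25 days: m = 7 gives 72.0% (THS); 8 gives 68.0% (Dual); 17 gives 8/25 = 32.0% (Dual); 18 gives 7/25 = 28.0% (CC).

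**Range over r, 30-day period**

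| Missing days | r=0.5 | r=0.75 | r=1.0 | r=1.25 | r=1.5 |
|---|---|---|---|---|---|
| 8 | 57.9 Dual | 67.3 Dual | 73.3 THS | 77.5 THS | 80.5 THS |
| 10 | 50.0 Dual | 60.0 Dual | 66.7 Dual | 71.4 THS | 75.0 THS |
| 15 | 33.3 Dual | 42.9 Dual | 50.0 Dual | 55.6 Dual | 60.0 Dual |
| 20 | 20.0 CC | 27.3 CC | 33.3 Dual | 38.5 Dual | 42.9 Dual |

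At the smallest triggered gap (8 of 30) the general label changes only if r < (7/3)·8/22 = 0.85.

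**Detailed label.** Staying above 95% needs r > 19·m/(L−m). At 8 of 30 this is 19·8/22 = 6.9, so practically any triggered gap loses 'Primarily THS'. From reported days alone the same subject is at 100% whatever the gap.

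**Which outputs are reached**

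- PP tables: one filled day is at least 10 CC, above the limit of 2. Every triggered THS-arm subject is non-compliant and leaves the PP Set for that period, so none is relabelled there.
- Average and maximum daily use: SAP 12.5 takes these as recorded by the subject, and the fill is written only for categories and compliance.
- FAS: Table 15.2.4.50 and topography by product use category (Figure 15.1.2.18) carry no condition. Tables 15.2.2.4.2 and 15.2.2.5.2 are produced only if the FAS differs from the Safety population by more than 10% (SAP 12.5).
- Safety Population category tables of SAP 12.5: the SAP does not say whether these exposure tables count as safety summaries. The safety rule covers the whole ambulatory interval, while SAP 12.1.1 plans category summaries by period.

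**The case against.** The strongest reply is that the rule is explicit, applies only past a threshold, and works against the sponsor's product. Non-completion may well reflect relapse, and the endpoint itself is the number of products used, which is summarised as recorded and listed. Where a visit date is missing, SAP 12.1.5 also caps the period at discharge. All of this stands. It confines the problem to the derived categories and supports keeping the fill as a worst case. It does not justify using the fill as the only FAS description of reported patterns.

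A reader might infer more than the documents support:

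- *That every such subject is relabelled.* At r = 1 the general label changes only when more than 30% of days are missing.
- *That the primary analysis or PP product-use tables are distorted by relabelling.* Triggered subjects are not in the PP Set for that period.
- *That relapse in the SA arm is overstated through the categories.* The category rule is worded as a THS percentage, while SA categories rest on abstinence (SAP 6.3.3.2). The clear effect there is through compliance.
- *That this rule alone makes labels differ between safety and other tables.* Safety categories span the whole ambulatory period and the others are by period, so labels can differ even with a complete diary.
- *That the reported dual rate rises by a known amount.* Neither a gap rate nor a true dual rate is given. The Dual count need not even rise: a subject with a 40% reported THS share, total use at baseline level and 10 of 30 days missing falls to 0.40·20/30 = 26.7%, which is CC.

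**Conclusion.** The point holds in limited form. The fill can only lower a subject's THS share, so labels can move only toward CC, and a THS-arm subject with no reported cigarettes can appear as Dual or CC in the FAS category summaries. The thresholds of 10 and 21 missing days of 30, and 8 and 18 of 25, rest on r = 1 and on zero THS for filled days. At half a 30-day period missing, every r from 0.5 to 1.5 gives Dual. How far the dual-use distribution shifts cannot be computed from the documents. The point bears on the description of a secondary objective and leaves the primary test unchanged. It is a worthwhile, inexpensive improvement.

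**What to change.** - In SAP 12.1.5, keep the baseline-CC fill for compliance and PP eligibility.
- For descriptive product-use categories, compute the THS percentage from reported days. Show subjects who meet the gap trigger in a separate 'insufficient diary data' row.
- Present the baseline-CC classification as a sensitivity table.
- State which rule governs the Safety Population category tables of SAP 12.5.
- Amend SAP 6.3.3.1, which ties the PP Set to the detailed categories, so that PP eligibility rests on the compliance rule.

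The cost is SAP wording, one extra row and one sensitivity table; no new data are needed. The downside is that some subjects are unclassified in the main table.
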